There is increasing evidence showing associations between PFAS and markers of glucose homeostasis and insulin resistance, and associations with adult type 2 diabetes risk in men and women (Cardenas 2017; He 2018; Sun 2018); strengthening the case for adverse metabolic activity of these compounds.

Roles of inflammatory cytokines and adipokines have been explored several studies of liver disease such as non-alcoholic fatty liver disease/steatohepatitis and in atherosclerosis (Hennig 2007, Wahlang 2016, Clair 2018). Proinflammatory responses, alteration in leptin signaling, and increases in TNF-alpha and IL-2 were reported in mechanistic studies with various persistent organohalogen pollutants in relation to diabetes and metabolic syndrome (Ferrante 2014; Wieser 2013). These associations have not yet been explored specifically with PFAS compounds. Some positive associations have also been found for cancer outcomes; with C8 studies finding strong
 associations for liver, kidney, and testicular cancer (Alexander and Olsen 2007; Barry2013; Bonefeld Jorgensen2014; Hardell2014; Steenland2015).

Some studies have found no association between PFAS exposure and health effects such as specific cancers (Alexander and Olsen 2007; Lundin 2009), lipids or metabolic function (Fisher, 2013). Effects of counfounding, bias, and chance on observed associations with PFAS compounds were explored in reviews of immune and cancer outcomes (Chang 2014, Chang 2015) and in studies of PFAS and menopause and endometriosis (Dhingra 2017, Ruark 2017, Ngueta 2017).

Few studies have evaluated PFHxS exposures and the risk of cancers and other adult diseases. Although 9 10 epidemiological studies have primarily evaluated PFOA and PFOS, there remain considerable data gaps 11 concerning the health effects of exposures to these chemicals in adults. There have been inconsistencies 12 in findings across studies and limited sample sizes in some studies. For some adverse outcomes, only one or a few studies have been conducted. Finally, except for the C8 studies, there are no published individual-13 14 level epidemiological studies in adults that have evaluated the health effects from exposures to PFAS-15 contaminated drinking water. Therefore, additional research is necessary to determine whether drinking 16 water exposures to PFHxS, PFOS, and PFOA increase the risk of non-cancer diseases. The proposed scope 17 of the funding and sample size estimated for this health study would be too small and insufficient to evaluate cancer health outcomes. 18

19 **2.5.2 Hypotheses**

For children (aged 4-17 years), the Multi-site Study will evaluate the following main hypotheses, following
the outline of the biochemical analytical plan (**Attachment 2**):

22

23 Higher serum levels of PFOA, PFOS, PFHxS, or other PFAS are associated with:

- Lipids (higher total cholesterol, low-density lipoprotein, and triglycerides, and higher prevalence
 of hypercholesterolemia; higher prevalence of obesity).
- Impaired renal function (a higher level of uric acid, a higher prevalence of hyperuricemia, and a
 lower estimated glomerular filtration rate (eGFR).

1	3.	Liver function/damage biomarkers (alanine transaminase (ALT), γ -glutamyltransferase (GGT),
2		direct bilirubin, cytokeratin-18 (CK-18)), and non-alcoholic fatty liver disease/steatohepatitis.
3	4.	Glycemic parameters (glucose, insulin, glycosylated hemoglobin (HbA1c), auto-antibodies
4		[glutamic acid decarboxylase (GAD-65) and islet antigen 2 (IA-2)], C-peptide, pro-insulin) and
5		diabetes (type 1 and 2).
6	5.	Measures of thyroid function (differences in thyroid stimulating hormone - TSH, total thyroxin -
7		TT4, free thyroxin - FT4, and TT3; higher prevalence of hypothyroidism/hyperthyroidism).
8	6.	Differences in sex hormones, growth and sexual maturation (testosterone, estradiol, and sex
9		hormone-binding globulin (SHBG); insulin-like growth factor - 1 (IGF-1), age at menarche, delayed
10		puberty).
11	7.	Immune response including prevalence of hypersensitivity-related outcomes (e.g., asthma, atopic
12		dermatitis; higher levels of immunoglobulins (IgG, IgA and IgM) and lower antibody responses to
13		rubella, mumps, and diphtheria vaccines).
14	Neuroo	developmental outcomes (lower intelligence quotient (full scale IQ), attention-deficit and
15	hypera	ctivity disorder (ADHD).
16	For adu	ults (aged \geq 18 years), the Multi-site Study will evaluate the following main hypotheses.
17	Higher	serum levels of PFOA, PFOS, PFHxS, or other PFAS are associated with:
18	1.	Lipids (higher total cholesterol, low-density lipoprotein and triglycerides) and a higher prevalence
19		of hypercholesterolemia).
20	2.	Higher prevalence of coronary artery disease and hypertension (including hypertensive disorders
21		of pregnancy).
22	3.	Renal function (higher level of uric acid and a higher prevalence of hyperuricemia, lower
23		estimated glomerular filtration rate (eGFR)) and higher prevalence of kidney disease.
24	4.	Glycemic parameters (glucose, insulin, glycosylated hemoglobin (HbA1c), auto-antibodies (GAD-
25		65 and IA-2), C-peptide, pro-insulin) and diabetes (type 1 and 2).
26	5.	Differences in thyroid hormones (thyroid stimulating hormone (TSH), TT4, FT4, and TT3), and
27		higher prevalence of hypothyroidism/ hyperthyroidism.

1	6.	Liver function/damage biomarkers (alanine transaminase (ALT), γ -glutamyltransferase (GGT),
2		direct bilirubin, cytokeratin-18 (CK-18)) and liver disease.
3	7.	Higher prevalence of osteoarthritis and osteoporosis.
4		
5	8.	Higher prevalence of endometriosis.
6	9.	Measures of immune response and inflammation (serum levels of IgA, IgE, IgG, IgM, C - reactive
7		protein (CRP), antinuclear antibodies (ANA), inflammatory cytokines and adipokines (interleukin
8		1- β (IL-1 β), interleukin 6 (IL-6), interleukin 8 (IL-8), monocyte chemotactic protein-1 (MCP-1),
9		tumor necrosis factor α (TNF α), leptin, adiponectin, resistin, plasminogen activator inhibitor-1
10		(PAI-1).
11	10	Higher prevalence of autoimmune diseases such as ulcerative colitis, rheumatoid arthritis, lupus,
12		and multiple sclerosis.
13		
14	2.6 Int	ended Use of Study Findings
14	2.0 m	
15	Given t	hat epidemiological research on the health effects of drinking water exposures to PFAS other than
16	PFOA i	s at an early stage, the Multi-site Study should make an important contribution to the scientific
17	literatu	ire, expand knowledge in this field, and help addressing concerns about past exposure.
18	Additic	mally, the Multi-site Study will provide the PFAS serum level and the results of the clinical tests and
19	effect	biomarker tests to each study participant. The participant can use this information for medical
20	decisio	n-making. Advice and assistance (e.g. workshops and or training programs) to clinicians in each
21	comm	unity be provided by recipients and ATSDR as a part of the community engagement efforts to be
22	able to	answer questions about the potential effects of elevated PFAS levels on health, interpreting
23	results	, additional test or treatments. ATSDR will provide summaries of the study findings to the
24	partici	pating affected communities and will also provide assistance in interpreting each of these results.
25		
23		
26		

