function	C8 1.078 1-5 yrs	2.3% change (mean difference = 0.17 µg/dI)	levels were about 20 $\mu g/L$ SD for TT ₄ as	
114	3,132 6-10 yrs		estimated at 1.4.	
	6,447 >10 - 17 yrs		Percent change in	
			TT ₄ was converted to	
			mean difference	
			assuming the	
			median TT_4 was ref.	
Thyroid			Provalence-0.6%	>16 000/stratum
disease		(PFOS: OR < 1.0)	(used PEOA results)	210,000/stratum
Uric Acid	Kataria 2015,	PFOS: 4 th vs 1 st guartile =	Mean PFOS serum	556/stratum
	NHANES	+0.19 mg/dL	level = 12.8 μg/L. SD	,
	1,960; 12-18 yrs		= 1.19.	
Hyperuricemia	Geiger 2013,	PFOS: 4 th vs 1 st quartile,	Mean PFOS serum	400/stratum
	NHANES	OR=1.65	level =16.6.	
	1,772; 12-18 years		Prevalence=16%	
eGFR	Kataria 2015	PFOA mean serum level	Standard	275/stratum
	1,960; 12-18 yrs	=3.5 μg/L. mean	deviation=27.6	
		difference= -6.6		
Testosterone	Lopez-Espinosa 2016,	PFOS (IQR):	Percent change was	Boys: 404/stratum
	C8	-5.8% boys (diff=1.9)	converted to mean	Girls: 368/stratum
	1,169 boys; 6-9 yrs	-6.6% girls (diff=2.45)	difference assuming	
	1,123 girl; 6-9 yrs		median testosterone	
			level was ref. level.	
			SD estimated at	
			9 63 for hovs	
IGF-1 (Insulin-	Lopez-Espinosa 2016.	PFHxS (IQR):	Percent change was	146/stratum
like growth	C8	Boys: -2.5% (diff=17.3)	converted to mean	,
factor – 1)		Girls: -2.1%	difference assuming	
			median IGF-1 in boys	
			as ref. level. SD	
			estimated as 52.6	
Delayed	Lopez-Espinosa 2011.	PFOS: mean serum level	OR for delayed	to calculate sample size,
Puberty	3 072 hove 8-18 vrs	was about 19 µg/L.	puberty and the	but sample sizes in this
	2.903 girls, 8-18 yrs		delayed puberty had	study were enough for sufficient precision
	-,000 8		narrow Cls	
ADHD	Stein 2011, C8	PFHxS mean serum level		
	10,546; aged 5-18	was 5.2 µg/L. 4 th vs 1 st		
	yrs.	quartile,	Prevalence:	764/24224
		0K=1.5	AUHU UX: 12.4%	764/stratum
Asthma	Stein 2016, NHANES	PFOA mean serum level =	Prevalence = 11%	2,400/stratum
	640; 12-19 yrs	3.6 μg/L.		
		OR=1.2		
Atopic	Wang 2011 (Taiwan)	PFOS mean serum	Prevalence=10.7%	220/stratum
dermatitis	244; infants, 2 yrs	level=5.5 μg/L., 4''' quartile OR=2 19		
Obesity	Karlsen 2017	PFOA mean serum	Prevalence=17%	250/stratum
	(Faroes)	level=2.22 μg/L. OR=1.88		

1 Note: Observed effect sizes focused on the results for serum levels of PFOS and/or PFHxS.

¹ eGFR –estimated glomerular filtration rate, TT4 – total thyroxine; IGF-1 – insulin-like growth factor 1; ADHD – attention-deficit
 and hyperactivity disorder.

4

5 3.3.2 Adults

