 current contact information for results reporting and potential future contact (Attachment 10).

The study staff will request that the adult participant and the parent of the child participant bring all
current prescription and over the counter medications prior to the study office. This will help the study
staff to complete the medications list (Attachment 11).

9 **3.6.4 Body and Clinical Measurements**

Trained study staff will perform the body and clinical measurements and specimen collections as
 described in the Manual of Procedures (Attachment 12).

12 Body Measurements: Trained study staff will perform body measurements, blood pressure 13 measurements, and blood draws. Three blood pressure (BP) measurements will be taken and averaged. The measured BP level is subject to biological and observer variability; therefore, the study will use three 14 15 different sizes of the manual cuffs in the measurements; the appropriate cuff size will be selected for each 16 participant and administered 3 times. The purpose of a specific measurement protocol, or training and 17 certifications of technicians and of ongoing quality control is to minimize variability due to known 18 exogenous factors and to reduce imprecision and biases in measurement. Measurement of resting blood 19 pressure, height, weight, and waist and hip circumference can occur in any order, but the BP 20 measurement should occur after the subject has been in the seated position for at least five minutes. BP 21 measurement will occur before venipuncture if the activities are scheduled consecutively. Trained study 22 staff will record the measurements in the Body and Blood Pressure Measures Form (Attachment 13).

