Attachment 3 – Justification for Sample Size Calculations (Supporting information)

- Attachment 3a Child Sample Size Calculations
- Attachment 3b Adult Sample Size Calculations

Sample size calculations were conducted using OpenEpi Version 3.03 (Dean AG, Sullivan KM, Soe MM. OpenEpi: Open Source Epidemiologic Statistics for Public Health, www.OpenEpi.com, updated 2014/09/22). For some health-related endpoints, calculations could not be conducted because of a lack of information in the studies on the parameters needed to make the calculations.

Sample size calculation for mean difference:

$$n_{1} = \frac{(\sigma_{1}^{2} + \sigma_{2}^{2} / \kappa)(z_{1-\alpha/2} + z_{1-\beta})^{2}}{\Delta^{2}}$$
$$n_{2} = \frac{(\kappa * \sigma_{1}^{2} + \sigma_{2}^{2})(z_{1-\alpha/2} + z_{1-\beta})^{2}}{\Delta^{2}}$$

The notation for the formulae are:

$$n_1 = \text{sample size of Group 1}$$

 $n_2 = \text{sample size of Group 2}$
 $\sigma_1 = \text{standard deviation of Group 1}$
 $\sigma_2 = \text{standard deviation of Group 2}$
 $\Delta = \text{ difference in group means}$
 $\kappa = \text{ratio} = n_2/n_1$
 $Z_{1-\alpha/2} = \text{two-sided Z value (eg. Z=1.96 for 95\% confidence interval).}$
 $Z_{1-\beta} = \text{power}$

Where N_2/N_1 is the ratio of the two sample sizes. Then N_2 is simply this ratio multiplied by N_1 . For a type 1 error (or α error) of .05, the $Z_{1-\alpha/2}$ value is 1.96. This calculation is for a two-tailed hypothesis test and equivalent to using a 95% confidence interval to determine statistical significance. For a one-tail test with α =.05, the $Z_{1-\alpha/2}$ in the above equation is replaced by $Z_{1-\alpha}$ and its value is 1.65, equivalent to using a 90% confidence interval to determine statistical significance. For 80% confidence interval to determine statistical significance. The $Z_{1-\beta}$ in the above equation is the Z value for the selected power. For 80% power, $Z_{1-\beta} = 0.84$, for 90% power, $Z_{1-\beta} = 1.28$, and for 95% power, $Z_{1-\beta} = 1.65$. (See Rosner B. Fundamentals of Biostatistics, 7th Edition, equation 8.27, p. 302).

Fleiss JL. Statistical Methods for Rates and Proportions. John Wiley & Sons, 1981.

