Attachment 3a. Sample Size for Child Study

The following notes provide comments and information on the parameters (e.g., standard deviation, disease prevalence) used in the sample size calculations provided in Table 1 for the children study.

Sample size calculations were conducted with type 1 (" α error") set at .05 and type 2 error (" β error) set at .20. Sample sizes per stratum group were calculated. It was considered important that a study have a total sample size so that exposures could be categorized into tertiles (i.e., reference level, medium level, and high level) or quartiles (i.e., reference level, low, medium and high).

Studies were selected that were considered the most representative of U.S. populations exposed via drinking water to PFOA, PFOS and/or PFHxS as a result of the migration of these PFAS chemicals into ground water or surface water sources from the use of aqueous film forming foam (AFFF). The PFOS, PFOA and PFHxS results in the NHANES studies were used in many of the sample size calculations. For those outcomes not included in NHANES studies, the C8 studies were used. Where applicable studies from Taiwan or other major industrialized countries were also used.

Examples:

Lipids

In the C8 study (Frisbee 2010), the mean total cholesterol level in the study population was 160.7 mg/dL and the standard deviation (SD) was 29.3. The sample size calculations assumed the same SD in children exposed and the unexposed group. For hypercholesterolemia (total cholesterol \geq 170 mg/dL), the prevalence in the C8 study was 34.2%.

Uric Acid

In the NHANES study (Geiger 2013), the mean uric acid level in the study population was 5.07 mg/dL with a SD of 1.19. The sample size calculations assumed the same SD in the exposed children and the unexposed group. The prevalence of hyperuricemia (uric acid \geq 6 mg/dL) in the NHANES study was 16%.

Kidney Function

The mean estimated glomerular filtration rate (eGFR) in the C8 study of children and adolescents (Watkins 2013) was 133 mL/min/1.73 m² with a SD of 23.9. The sample size calculations assumed the same SD in the exposes children and the unexposed group.

Attention Deficit/Hyperactivity Disorder (ADHD)

In the C8 study (Stein 2011), the prevalence of participant-reported ADHD was 12.4% and the prevalence for participant-reported + used medications for ADHD was 5.1%. Sample size calculations used the 12.4% prevalence.

Hypersensitivity-related Outcomes

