Assuming a 95% CI and 95% power, the sample size = 68/group.

a. TSH

In Ji 2012, the sample size was 633, \geq 12 years of age and the median TSH level was 1.37 µIU/mL with an IQR of 0.90, 2.01. The standard deviation was estimated as the IQR range divided by 1.35: (2.01 - .90)/1.35 = 0.82. This standard deviation was assumed for each group. For TSH, the linear regression coefficients for PFOS and PFHxS were 0.062 and 0.013, respectively. Using a PFOS level of 15 ng/mL and a PFHxS level of 9 ng/mL, the mean difference for PFOS and PFHxS are 0.93 and 0.12, respectively.

Assuming a 95% CI and 80% power, the sample size = 13/group for PFOS

Assuming a 95% CI and 80% power, the sample size = 733/group for PFHxS

b. TT₄ (total thyroxine)

In Ji 2012, the sample size was 633, \geq 12 years of age and the median TT₄ level was 7.4 µg/dL and the IQR was 6.7, 8.1. The standard deviation was estimated: (8.1 – 6.7)/1.35 = 1.04. This standard deviation was assumed for each group. For TT₄, the linear regression coefficients for PFOS and PFHxS were -0.021 and - 0.007, respectively. Using a PFOS level of 15 ng/mL and a PFHxS level of 9 ng/mL, the mean difference for PFOS and PFHxS are -0.32 and -0.06, respectively.

Assuming a 95% CI and 80% power, the sample size = 166/group for PFOS

Assuming a 95% CI and 80% power, the sample size = 4,716/group for PFHxS

Sample sizes for the categorical outcomes in Table 2 were based on the following prevalences in adults:

Hypercholesterolemia: 15% Hyperuricemia: 24% Thyroid disease: 6.5% (reported and confirmed by medical records); 11.5% (reported only) Elevated ALT: 11.2% Elevated GGT: 14% Elevated bilirubin: 1.1% Osteoporosis: 5% Osteoarthritis: 7.6% Cardiovascular disease: 13% Ulcerative colitis: 0.5% Rheumatoid arthritis: 1.2%

Health related Endpoints Not shown in Table 2:

Chronic kidney disease: 1.4% Liver disease: 2% Hypertension: 37% Pregnancy-induced hypertension: 8.5% Endometriosis: 7% Lupus: 0.2% Multiple sclerosis: 0.32% Kidney cancer: 0.3%

Multi-site Study – Eligibility Screening Script

Multi-site Study Eligibility Screening Script Flesch-Kincaid Readability Score – 5.8

> Form Approved OMB No. 0923-XXXX Exp. Date xx/xx/201x

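### Child adiposity is measured on a continuous scale but enters the hypotheses only as prevalence of obesity; a BMI-for-age z-score should be added as a companion outcome

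*Protocol*

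**What the plan says.** In protocol section 2.5.2, the children's hypothesis 1 lists lipid levels, hypercholesterolemia and "higher prevalence of obesity". No child hypothesis names BMI, waist or any other continuous measure of body size. By contrast, the same section gives cholesterol, uric acid and thyroid hormones both as a level and as a category.

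Section 3.6.4 provides for height, weight, waist and hip to be measured by trained staff under a common protocol with quality control, and Attachment 13 has a field for BMI. Obesity is also asked of the parent as a diagnosis (Attachments 15 and 15a, item F1) and appears on the child record abstraction form (Attachment 17b).

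The obesity row of Table 1 gives "level=2.22 μg/L. OR=1.88" and "Prevalence=17" (per cent), with 250 per stratum. Section 3.10 assigns linear regression to continuous effect biomarkers, and logistic regression to categorised biomarkers or disease prevalence. Section 3.7 lists blood analytes as the biomarkers.

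For adults, hypothesis 2 reads "Higher prevalence of coronary artery disease and hypertension (including hypertensive disorders" of pregnancy. Section 3.6.4 adds "Three blood pressure (BP) measurements will be taken and averaged". Section 3.6.5.2 obtains hypertension as an ever-had condition in the questionnaire, to be confirmed from medical records. Attachment 3b gives "Hypertension: 37" (per cent) among endpoints outside Table 2, with no odds ratio, standard deviation or stratum size.

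**The concern.** A cut at 17% prevalence keeps only which side of a threshold a child falls on. All variation among the non-obese children, the large majority, is discarded, although the measurement exists and has been standardised. A modest shift in BMI across exposure strata could be well within reach of 2,000 children on the continuous scale and yet be estimated imprecisely as an odds ratio for obesity.

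The protocol gives no reason for treating adiposity differently from the outcomes it hypothesises on both scales, and its own review of child health effects (2.5.1.1) cites indicators of adiposity as linked with PFAS. Because BMI is not among the effect biomarkers of 3.7, the analysis section does not clearly give it a model either.

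**Working it through.** **Inputs.** Alpha "set at .05 and type 2 error" .20 (Attachment 3a); two-sided, since Attachment 3 says "This calculation is for a two-tailed hypothesis test and equivalent to using a 95% confidence interval to determine statistical significance"; reference prevalence p0 = 0.17 and odds ratio 1.88 (Table 1); 2,000 children (3.3.1), so 2,000/4 = 500 per quartile.

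**Step 1: reproduce the plan's figure.** The exposed prevalence is p1 = 0.17 × 1.88 / (0.83 + 0.17 × 1.88) = 0.278. The mean prevalence is 0.224. The pooled-variance (Fleiss) formula is

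n = [1.96 √(2 × 0.224 × 0.776) + 0.8416 √(0.17 × 0.83 + 0.278 × 0.722)]² / 0.108² ≈ 233.

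With the continuity correction this becomes 251, which matches the stated 250.

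**Step 2: the same contrast on a continuous scale.** Assume a normal trait with equal SD in both strata and a pure location shift. The shift is d = z(0.83) − z(0.722) = 0.954 − 0.589 = 0.365 SD. The size for 80% power is 2 × (1.96 + 0.8416)² / 0.365² ≈ 118 per stratum. The like-for-like comparison is 233 against 118, because the 251 carries a continuity correction and the 118 does not.

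**Step 3: power at Table 1's 250 per stratum.**
- Binary: Φ{[0.108 √250 − 1.96 √(2 × 0.224 × 0.776)] / √(0.17 × 0.83 + 0.278 × 0.722)} = Φ(0.944) = 82.8%.
- Continuous: Φ(0.365 √(250/2) − 1.96) = Φ(2.125) = 98.3%.
- Gain: 15.6 points before rounding. If the odds ratio is converted with a logistic scale instead (d = ln 1.88 × √3/π = 0.348), continuous power is 97.3%.

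**Step 4: power at the 500 per quartile that 2,000 children give.** The same formulas apply. The odds ratios below 1.88 are assumptions, shown as a range.

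| Odds ratio | Shift (SD) | Binary | Continuous | Gain (points) |
|---|---|---|---|---|
| 1.88 | 0.365 | 98.4% | 99.99% | 1.6 |
| 1.5 | 0.232 | 72.6% | 95.6% | 23.0 |
| 1.4 | 0.192 | 55.7% | 85.7% | 30.0 |
| 1.3 | 0.149 | 36.8% | 65.2% | 28.4 |

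**Step 5: adult hypertension.** The plan gives a prevalence of 37% and nothing else from which power could be computed, and the outcome is a reported diagnosis checked against records. No comparison follows from the plan's figures, so none is claimed.

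**The case against.** Several objections carry weight.

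*The scope of the hypothesis list.* Section 2.5.2 lists main hypotheses, and the methods in 3.10 are worded as an open list. Nothing forbids a linear model of BMI, and an analysis plan not shown here may contain one. This stands: the point concerns what the protocol's hypotheses name, and it does not show that BMI will go unanalysed.

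*The stratum size.* The 250 in Table 1 is a required minimum, not the size expected. At 500 per quartile and the plan's own odds ratio the gain is negligible. This also stands. The larger gains need a smaller true odds ratio than the plan assumes. That is plausible, since Table 1 uses 1.2 for asthma and 1.5 for ADHD, and section 3.3.2 warns that actual differences may depart from the literature. It remains an assumption.

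*Consistency and power.* The protocol wants methods comparable with earlier PFAS research, and section 1.1.3 says endpoints were not chosen on power. That supports keeping obesity prevalence, but it is no reason to omit the continuous measure beside it.

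*The planned analysis.* Exposure will also be modelled continuously and with splines, and section 3.10 does not rest interpretation on significance alone. The two-stratum contrast is therefore a guide to lost information, not a forecast of the study's results.

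A reader might infer that adult hypertension loses power in the same way because three pressures are averaged. The documents do not support that. Hypertension here is an ever-had diagnosis and includes hypertensive disorders of pregnancy. A single-visit pressure, lowered by treatment in some participants, is a different outcome and not the uncut form of the same one.

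**Conclusion.** The concern holds for child adiposity. A measured continuous trait is represented in the hypotheses only by a dichotomy, unlike comparable outcomes in the same list. The cost is about 16 points of power at Table 1's minimum of 250 per stratum (83% against 98%). At 500 per quartile it is about 2 points if the odds ratio is 1.88, and about 23 to 30 points if it is 1.3 to 1.5.

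These sizes rest on a normal trait, equal SDs, a pure shift, an unadjusted comparison of two strata, and 17% taken as the reference-stratum prevalence. The documents do not state the distributional assumptions. A reader might infer a loss of 15 points or more whatever the stratum size or true effect, or for hypertension as well; neither follows. This is an inexpensive improvement to the plan, not an error in its sample size.

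**What to change.** In section 2.5.2, children's hypothesis 1, add BMI-for-age z-score, and waist circumference, from the measured values as continuous outcomes. In section 3.10, extend the linear regression sentence to name them. Keep obesity prevalence as the companion binary outcome, and state whether it is defined from measured BMI or from the reported diagnosis.

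Mean measured systolic and diastolic pressure may be added as a separate secondary adult outcome. The protocol should then state how antihypertensive use, recorded in the Attachment 11 medication list, is handled in that analysis, and should keep the outcome distinct from diagnosed hypertension.

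The cost is a few lines of text and a few more models, with the added multiplicity that brings, plus one assumption about treated pressure if the adult outcome is taken up. No new data are needed.
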